9.7 Quality of Life

9.7.1 Primary QOL Endpoints

Quality of life assessment is performed in an identical fashion in both arms A and B and will be administered to both arms on the same schedule and frequency. The QOL assessment utilizing the FACT-

FWB+PWB and MMS instruments will first be administered at registration (+ 7 days) prior to initiation of treatment or observation. During the treatment or observation period, QOL will be measured every 6 cycles (day end + 7 days) and at the end of treatment or observation (+ 14 days). For patients that discontinue protocol therapy or go off observation early not due to disease progression, QOL will also be assessed at the next quarterly Long Term follow-up visit (+ 14 days). After this, these patients will not be followed further for QOL. Patients will be asked to complete the QOL questionnaire just prior to meeting with health care providers at scheduled visits. This should reduce the impact of health care related information upon perceived QOL.

The FACT-FWB+PWB PRO instrument has 14 items and the score ranges from 0-56. The primary endpoint for the QOL study will be defined as the mean change of the FACT-FWB+PWB score from registration (prior to randomization) to cycle 24. The null hypothesis is that the FACT-FWB+PWB mean change score between the two groups is the same over this time period. Based on the length of this PRO instrument, a minimal absolute difference in means change scores of the two arms of 4-6 is considered clinically significant between two groups.(70) Nevertheless, for this analysis the difference in drug-related QOL must be much greater to overcome a significant PFS benefit. The FACT- FWB+PWB domains are reported to have a standard deviation (SD) of 11. (Personal Correspondence with [name] dtd 12.26.08)

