Differences in FACT-FWB+PWB mean change scores between the treatment arms from time of registration to cycle 24 that can be detected with 80% power are presented in following table. The expected hazard rates on each arm served to establish patients alive without PD at the end of the interval. Sensitivity for the % of patients alive without PD (n=55 patients given expected hazard rates) assumed to complete the questionnaire at the end of cycle 24 (compliance rates of 55%, 70%, 85%), allowing for slightly more variability in the instrument (11.0, 12.0) and assuming different correlation (0.4, 0.6, 0.8) between repeated measures was performed. For example, assuming a SD of 11.0 for the FACT-FWB+PWB, a correlation between repeated measures of 0.6 and using a two-sided t-test with a 0.05 significance level, there is sufficient power to detect a true difference in the FACT-FWB+PWB mean change score between the two arms of 7.3-9.2. Given our chosen interval for the primary endpoint and the reduced sample size with the redesign, we will only be able to detect large differences in mean change score between arms at expected compliance rate (70%).

Differences detected with 80% power between Treatment Arms in Mean Change Score from Registration to end of Cycle 24: FACT-FWB+PWB					
standard deviation (SD)	correlation	SD of change	55% compliance n=30	70% compliance n=38	85% compliance n=56
11.0	0.4	12.05	11.2	9.9	9.0
	0.6	9.84	9.2	8.1	7.3
	0.8	6.96	6.5	5.7	5.2
12.0	0.4	13.15	12.2	10.8	9.8
	0.6	10.73	10.0	8.8	8.0
	0.8	7.59	7.1	6.2	5.7

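### Section 9.7.1: the QOL detectable differences do not follow from the stated 80% power, two-sided 0.05 t-test and n, and the n=56 header exceeds the 55 patients available

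*Combined protocol and SAP*

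**What the plan says.** Section 9.7.1 defines the primary QOL endpoint as the mean change in FACT-FWB+PWB from registration to cycle 24. Its table is titled "Differences detected with 80% power between Treatment Arms in Mean Change Score from Registration to end of Cycle 24". The worked example takes SD 11 and correlation 0.6, "using a two-sided t-test with a 0.05 significance level", and concludes that "there is sufficient power to detect a true difference in the FACT-FWB+PWB mean change score between the two arms of 7.3-9.2".

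The sample size starts from "patients alive without PD (n=55 patients given expected hazard rates" (55 patients), to which compliance of 55%, 70% and 85% is applied. The column headers give n=30, n=38 and, for the last, "85% compliance n=56". The section does not say whether n is per arm or the total of both arms. On the source of the 55 it says only: "The expected hazard rates on each arm served to establish patients alive without PD at the end of the interval".

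It then concludes that "we will only be able to detect large differences in mean change score between arms at expected compliance rate (70" (that is, 70%). The benchmark is that "a minimal absolute difference in means change scores of the two arms of 4-6 is considered clinically significant". The same paragraph adds that the difference would have to be much larger than this to outweigh a PFS benefit.

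**The concern.** Power, test, alpha, SD, correlation and n are all given, so each cell can be recomputed. The cells do not come out. The 85% header is impossible on its face, because a fraction of 55 patients cannot be 56.

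This is the plan's only statement of what the primary QOL comparison can detect. As written, a reader cannot tell which alpha or which n it applies to. On one reading of n the table is too pessimistic, and on the other too optimistic. A null QOL result would therefore be misjudged as to what it rules out.

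**Working it through.** **Inputs.** From Section 9.7.1: 80% power; two-sided 0.05 t-test; SD 11 or 12; correlation r = 0.4, 0.6 or 0.8; 55 patients; compliance 55%, 70% and 85%. From Section 9.4: 90 patients per arm; monthly hazards 0.0279 (Obs) and 0.011 (R).

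**Header n.** 0.55 × 55 = 30.25; 0.70 × 55 = 38.5; 0.85 × 55 = 46.75. The headers 30 and 38 are these products cut to whole numbers, so the third should be 46. The printed values agree with this: for SD 11, r = 0.4, the first-to-last ratio is 11.2/9.0 = 1.24. √(46/30) is also 1.24, but √(56/30) = 1.37.

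**SD of change.** SD × √(2(1−r)) gives 12.05, 9.84 and 6.96 for SD 11, and 13.15, 10.73 and 7.59 for SD 12, as printed. This column is correct, so the discrepancy lies in alpha, power or n.

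**Detectable difference.** With m patients per arm, solve for δ in P(T > t₀.₉₇₅) = 0.80. Here T is noncentral t with 2m−2 degrees of freedom and noncentrality δ / (SD of change × √(2/m)). A close hand check is δ ≈ (t₀.₉₇₅ + t₀.₈₀) × SD of change × √(2/m). For SD 11, r = 0.6:

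- 30 per arm (m = 30): (2.002 + 0.848) × 9.84 × 0.258 ≈ 7.24
- 30 in total (m = 15): (2.048 + 0.855) × 9.84 × 0.365 ≈ 10.43
- printed: 9.2

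All cells at 80% power and two-sided 0.05, for n = 30 / 38 / 46:

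| SD | r | Printed | n per arm | n as two-arm total |
|---|---|---|---|---|
| 11 | 0.4 | 11.2 / 9.9 / 9.0 | 8.86 / 7.85 / 7.12 | 12.77 / 11.26 / 10.18 |
| 11 | 0.6 | 9.2 / 8.1 / 7.3 | 7.24 / 6.41 / 5.81 | 10.43 / 9.19 / 8.31 |
| 11 | 0.8 | 6.5 / 5.7 / 5.2 | 5.12 / 4.53 / 4.11 | 7.37 / 6.50 / 5.88 |
| 12 | 0.4 | 12.2 / 10.8 / 9.8 | 9.67 / 8.56 / 7.76 | 13.93 / 12.28 / 11.10 |
| 12 | 0.6 | 10.0 / 8.8 / 8.0 | 7.90 / 6.99 / 6.34 | 11.37 / 10.03 / 9.07 |
| 12 | 0.8 | 7.1 / 6.2 / 5.7 | 5.58 / 4.94 / 4.48 | 8.04 / 7.09 / 6.41 |

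None of the 18 cells matches on either reading, and using 56 in the last column does not change that.

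**Power of the printed differences at two-sided 0.05.** Per arm, it is about 94% at 30, 38 and 46, and 97-98% at 56. As a two-arm total, it is about 69-70% at 30, 38 and 46, and 78-79% at 56.

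**What reproduces the table.** With 80% power, two-sided 0.10 (equivalently one-sided 0.05) and two-arm totals of 30, 38 and 46, all 18 cells match to the printed decimal. SD 11, r = 0.6 gives 9.16 / 8.09 / 7.33. With 56 as the last total, only 12 match.

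**Is 55 per arm or a total?** At 24 months, 90 × exp(−0.0279 × 24) = 46.1 Obs patients and 90 × exp(−0.011 × 24) = 69.1 R patients are progression-free. The total is 115 and the harmonic mean 55.3. At 24 cycles of 28 days (22.1 months) the counts are 48.6 and 70.6, the total 119 and the harmonic mean 57.6. Using these unequal arms changes the per-arm SD 11, r = 0.6 row only slightly: 7.18 / 6.34 / 5.74 at 24 months and 7.03 / 6.21 / 5.63 at 22.1 months.

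**The case against.** The strongest reply is that the cause cannot be fixed uniquely and that the per-arm reading is not in the text. Several points are fair.

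- The count of zero matches rests on the exact t. With the normal approximation, the stated power and alpha, and 56 as a two-arm total, five of the six cells in the 85% column match (the miss is 7.37 against 7.3). No cell in the other two columns does.
- Other settings come close. Exact t at 90% power and two-sided 0.025, with 30, 38 and 46 per arm, matches 17 of 18. The normal approximation at 80% and two-sided 0.05, with compliance applied to a two-arm total of 66, matches 15 of 18 and would explain the 56. But it contradicts the stated 55 and the headers 30 and 38.
- The figure 55 arises from the hazards only at 24 calendar months with a harmonic mean. The simple per-arm mean is 57.6 there and 59.6 at 22.1 months.
- The 56 could be a misprint or a text-extraction fault.

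These points limit what can be said about how the table arose. They do not rescue it, because each near-fit departs from an input that Section 9.7.1 states. The mismatch in the 30 and 38 columns does not depend on the 56. Whichever averaging is used, a two-arm total of 55 is less than half of the 115-119 patients that the plan's own hazards imply.

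The practical conclusion also partly survives. In the worked example at 70% compliance, the detectable difference is 6.4 per arm, 8.1 as printed or 9.2 as a total. All three are above 4-6.

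**Conclusion.** The point holds and is minor. The table and the 7.3-9.2 sentence are wrong for their stated inputs, and n=56 is impossible given 55 patients. Against 80% power at two-sided 0.05 with 30, 38 and 46, the printed differences are 25-27% too large if n is per arm and 11-13% too small if n is a two-arm total.

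The per-arm reading is better supported, given exponential PFS at the Section 9.4 hazards and 90 patients per arm. That a per-arm count was entered as a total, with a different alpha, is an inference from the 18-cell match. The documents do not say so.

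On the per-arm reading at 70% compliance, the statement that only large differences can be detected holds for r = 0.4 and r = 0.6. At r = 0.8 the detectable difference (4.53-4.94) lies inside the 4-6 range. The printed 5.7 for SD 11 already did; on the two-arm-total reading the values (6.50-7.09) do not. The plan's own remark that a much larger difference would be needed to offset a PFS benefit keeps the consequence small.

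**What to change.** In Section 9.7.1:

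1. State alpha and sidedness with the table, and state that n is per arm.
2. Change the last header from 56 to 46.
3. Replace the 18 cells with the per-arm values tabulated above, and change 7.3-9.2 to about 5.8-7.2.
4. Qualify the large-differences sentence by correlation. At 70% compliance the detectable difference is 4.53-4.94 for r = 0.8, 6.41-6.99 for r = 0.6 and 7.85-8.56 for r = 0.4.

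If a two-arm total was intended, use the last column of that table (8.3-10.4 in the sentence) and reconcile 55 with the roughly 115 progression-free patients implied by Section 9.4. If one-sided 0.05 (two-sided 0.10) was intended, say so in both the text and the table.

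The cost is one table, its header and two sentences. Sample size, the PFS analysis and trial conduct do not change.

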9.7.2 Secondary QOL Endpoints

We will also explore the impact of the differential treatment survival (PFS) on the quality of life at certain clinically meaningful time points. More specifically, we will first evaluate the difference in the FACT-FWB+PWB mean scores between patients that experience disease progression (PD) and patients who do not experience PD using mixed effects model, where the longitudinal scores were collected from the following eight intervals:

- Interval 1: (registration prior to randomization – end cycle 6)
- Interval 2: (beg cycle 7 - end cycle 12)
- Interval 3: (beg cycle 13 - end cycle 18)
- Interval 4: (beg cycle 19 - end cycle 24)
- Interval 5: (beg cycle 25 - end cycle 30)
- Interval 6: (beg cycle 31 - end cycle 36)
- Interval 7: (beg cycle 37 - end cycle 42)
- Interval 8: (beg cycle 43 - end cycle 48)

Patients are included in the analysis of an interval if they have not failed up to the beginning of the interval. During an interval, for those patients that experience PD or discontinue treatment due to other reasons, the QOL assessment at the time of progression/ discontinuation will be used and for those who survive the interval, the QOL assessment at the end of the interval is used. We will also perform sensitivity for patients that did experience PD during the interval with respect to change in QOL status since last QOL assessment. Given the expected high level of missingness in the QOL data, we will analyze that data according to the methods described in Schluchter and in Schluchter, Greene and Beck.(71, 72)

These methods take into account the possibility of informative missingness by jointly modeling the longitudinal response (here, QOL scores) and the time to dropout.

9.7.3 Exploratory QOL Endpoints

For both the PACT-FWB+PWB and MMS subscales, we will provide descriptive statistics and calculate Chronbach's alpha to assess reliability. Further we will assess the differences in the MMS between the two arms at cycle 24 visit. We also are interested in the relationships between individual elements of the FACT-PWB+FWB and the MMS instrument and important clinical measures in an effort to discern criterion validity. We will segment patients into clinical groups such as ECOG performance status 0-1 vs 2 that we expect to have significantly different scores and analyze these relationships with 1-way multivariate analysis of variance (MANOVA). When MANOVA is significant then a univariate analysis of variance is done on each dependent variable.

Rev. 1/16

9.8 Correlative Studies

Phase II correlative samples will be used for descriptive stats, assay validation, and for preliminary feasibility purposes.

9.8.1 Gene Expression Profiling

GEP will be evaluated at baseline and post-treatment at time of progression (or at off-study if patients discontinue protocol therapy for reasons other than progression). For patients randomized to the lenalidomide arm, comparisons will be made of their baseline GEP versus their post-treatment sample drawn as described above at the time of progression or off-study. Data preprocessing is the first step in microarray data analysis. This entails background adjustment, normalization (e.g., scaling and quantile normalization), and summarization. These tasks can be accomplished using various software such as MAS 5.0 from Affy, or the R packages affy, affycomp, gcrma, and affyPLM. Exploratory analyses will then be performed to examine the underlying distributions using box plots, density plots, scatter plots, etc. Next differential expression analysis of the two groups (baseline vs. off-study) will be performed. Since statistical tests will be conducted upon tens of thousands of genes simultaneously, the false discovery rate (FDR) will be used to control the percentages of false positives among selected genes.(73) Relevant tools for differential expression analysis include permutation procedures, SAM,(74) empirical Bayes methods, q-value, etc.(75, 76) Once significant genes have been identified, hierarchical clustering analysis will be performed to investigate any relation among the selected genes.(77) In this context we will also evaluate the role of DKK1 expression.

All of our calculations for the GEP correlative endpoints assume samples are obtained from all patients. To evaluate GEP as a prognostic marker, we will evaluate the difference in PFS outcome by GEP-defined risk group (high-risk vs standard-risk) within each arm (R and Obs) and overall. The table below presents the PFS hazard ratios with GEP-defined high risk being an unfavorable subtype that can be detected with 80% power assuming a 5% level of significance and

9.8.2 Immune Function

In a recent SWOG study, immune function as measured by SOX-2 has been studied. In that patient population, a large difference in progression-free survival for SOX-2 positive versus SOX-2 negative patients was found. SOX-2 positive patients experience much longer progression-free survival (HR=0.15, p=0.01). In this study, we will evaluate whether this observation can be generalized. At baseline, approximately 2/3 of patients will be SOX-2 negative versus 1/3 of patients being SOX-2 positive. Given 33% prevalence of SOX-2 positive, analysis at 7.5y, and full sample yield, this study has 80% power to detect HR of 0.33, 0.43, and 0.50 or lower if the number of events in the R-treated arm are n=43 events, n=62 events, and n=80 events, respectively given 5% significance (0.38, 0.48 and 0.54 with 10% significance). Changes in immune expression with R therapy will be evaluated only by descriptive statistics for hypothesis generation.

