1.7.3 Immune Function

This trial provides an important opportunity to evaluate the changes in immune function as a result of lenalidomide therapy in early myeloma. Lenalidomide was developed in part due to its capacity to mediate greater co-stimulation of T cells compared to the parent compound, thalidomide. Several groups have now documented that progression of MGUS to MM is associated with changes in the function of both innate as well as adaptive immune effector cells. The underlying hypothesis is that lenalidomide will favorably impact these responses and this will correlate with clinical benefit in terms of PFS. Analyses of immune function will be carried out in the [name] lab, which has considerable experience with such studies. Certain aspects of immune response are of particular interest in this trial:

- Changes in NK and NKT number and activation
- Changes in effector (Th1, Th17), and regulatory (FOXP3+ tregs) T cells
- Changes in antigen specific immunity, particularly against stem cell associated antigens (e.g., SOX-2), shown to correlate with favorable outcome in these patients
- Changes in dendritic cell subsets

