2.2.3 Correlative Objectives

2.2.3.1 To evaluate the impact of therapy within GEP-defined risk groups and GEP as a prognostic marker.

2.2.3.2 To study the effects of lenalidomide on laboratory markers of immune function.

2.2.3.3 To study the prognostic value of MRI detected asymptomatic bone disease on clinical outcome.

Rev. 9/12

2.2.3.4 To evaluate the prognostic effect of baseline high-risk cytogenetic abnormalities on clinical outcome.

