10.3 Specimens for Immunology Testing – Yale University

Studies from the [name] lab and others have extensively characterized the changes in immune effector cells in MM. Immune system is currently thought to be a major target of these “immune modulatory drugs”, although the precise mechanism of the effects and their correlation with clinical outcome remains unclear. Most studies with revlimid in MM now utilize combination therapies. Therefore the effects of the drug are difficult to ascertain. As discussed

previously, this trial therefore provides an unprecedented opportunity to prospectively evaluate this issue in the context of a controlled study with single agent revlimid. Two aspects are of particular interest in this trial.

- Changes in antigen specific T cell function, particularly those against stem cell associated antigens such as SOX2, and selected cancer-testis antigens (7-9). T cell immunity will be analyzed using overlapping peptide libraries using methods as described previously.
- Changes in number and activation status of natural killer and natural killer T (NKT) cells, analyzed using flow cytometry, using methods as described previously by the [name] lab. (10,11)

The presence of spontaneous T cell immunity to SOX2, an embryonal stem cell antigen that marks putative stem cells in MM, correlates with risk of progression. We hypothesize that these features will correlate with response to Revlimid and risk of disease progression. Finally, this trial also provides an unprecedented opportunity to evaluate the changes in immune effector cells as well as changes in gene expression in response to single agent Revlimid in patients with early MM.

This analysis will be performed at Yale University, under the direction of [name].

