10.3.1 Sample Submission Schedule

Collect samples of peripheral blood and bone marrow aspirate at:

- Preregistration
- At study discontinuation or progression (whichever comes first)

NOTE: Pre-study samples for research should be collected at the same time as the diagnostic blood and bone marrow studies that are required to establish the diagnosis of myeloma and determine eligibility. Additional procedures to collect the research specimens should not be required.

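### Section 9.8.2 plans immune change in the lenalidomide arm only and sizes the SOX-2 analysis on that arm's events, although the same samples are scheduled in both arms

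*Combined protocol and SAP*

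**What the plan says.** The phase III correlative objective is "To study the effects of lenalidomide on laboratory markers of immune function" (2.2.3.2). Section 10.3 presents the trial as a chance to study this "in the context of a controlled study with single agent revlimid".

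Blood and marrow go to the immunology laboratory twice: at pre-registration, and at study discontinuation or progression, whichever comes first (7.2 and 10.3.1). Neither place limits this to one arm. Section 7 is headed for Arms A and B, and submission depends only on consent.

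Section 9.8.2 then contains two analyses:

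- **Immune change.** "Changes in immune expression with R therapy will be evaluated only by descriptive statistics for hypothesis generation".
- **SOX-2 and PFS.** The plan will examine whether an earlier SWOG finding (HR 0.15, longer PFS in SOX-2 positive patients) generalises. With 33% prevalence, analysis at 7.5 years and full sample yield, it claims 80% power for hazard ratios of 0.33, 0.43 and 0.50 "if the number of events in the R-treated arm are n=43 events, n=62 events, and n=80 events", respectively, at 5% significance.

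No observation-arm or between-arm immune analysis is specified in 9.8.2 or 10.3.

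**The concern.** The objective is about what the drug does, but the planned description has no comparator. Section 1.7.3 states that "progression of MGUS to MM is associated with changes in the function of both innate as well as adaptive immune effector cells". If that also applies to the step from smoldering to symptomatic disease, a sample taken at progression will show immune change whether or not the patient received lenalidomide. Seen in treated patients alone, a progression effect could pass for a drug effect, and a real benefit could be cancelled by progression and pass unnoticed.

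For SOX-2, the question is whether a baseline marker predicts PFS. Powering it on the arm expected to have fewer events leaves most of the available information unused.

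**Working it through.** **1. What the change score contains.** Let δ be the drug effect, π the shift that accompanies progression, τ(t) the drift with time to the second sample, and q the share of second samples taken at progression.

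- Mean change, lenalidomide arm: δ + q_R·π + τ(t_R)
- Mean change, observation arm: q_O·π + τ(t_O)
- Difference, all samples: δ + (q_R − q_O)·π + τ(t_R) − τ(t_O)
- Difference, progression samples only (both q = 1): δ + τ(t_R) − τ(t_O)

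The lenalidomide-only change cannot isolate δ. The all-samples difference still carries π if the arms differ in why patients stop, and only Arm A can stop for drug toxicity. The progression-only difference removes π but leaves timing, and it compares patients selected by an event after randomisation. It is better than the one-arm change, but it is not a clean randomised contrast.

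**2. Expected PFS events at month 90.** Inputs from 9.4: medians 24.8 and 62 months, 90 patients per arm, 45-month accrual (taken as uniform), exponential PFS. With λ = ln 2 / median, P(event) = 1 − [exp(−45λ) − exp(−90λ)] / (45λ).

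- Observation: λ = 0.02795, P = 0.838, 75.4 events
- Lenalidomide: λ = 0.01118, P = 0.525, 47.2 events
- Total 122.7, matching the 123 in 9.8.1

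The observation arm supplies 75.4 / 122.7 = 61% of the events. The 43, 62 and 80 scenarios come from 9.8.1: half of 123, less or plus 30%. The 62 and 80 scenarios exceed the 47 that the design implies for the lenalidomide arm.

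**3. Reproducing the plan's SOX-2 figures.** Split D events between SOX-2 positive (d₁) and negative (d₂) patients under the alternative, for 90 patients in one arm, 33% positive, with the same accrual and analysis time. Then I = 1/(1/d₁ + 1/d₂), and power = Φ(|ln HR|·√I − 1.96).

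| D | HR | d₁ / d₂ | Power |
|---|---|---|---|
| 43 | 0.33 | 7.6 / 35.4 | 79% |
| 62 | 0.43 | 14.6 / 47.4 | 80% |
| 80 | 0.50 | 23.0 / 57.0 | 80% |

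The stated hazard ratios reproduce as a single-arm, two-sided calculation. The plain Schoenfeld formula does not fit: it gives detectable values of 0.40, 0.47 and 0.51.

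**4. Same method, design-expected events** (full yield, two-sided 5%).

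- *Lenalidomide arm, 47 events, HR 0.50:* d₁ = 10.9, d₂ = 36.1, I = 8.40. Power = Φ(0.693 × 2.90 − 1.96) = Φ(0.05) = 52%. The HR detectable with 80% power is about 0.35 to 0.36 (prevalence 33% or one third).
- *Both arms pooled, 123 events, HR 0.50:* d₁ = 30.8, d₂ = 92.2, I = 23.1. Power = Φ(0.693 × 4.81 − 1.96) = Φ(1.37) = 91.5%. Stratifying by arm, I = 8.4 + 15.1 = 23.5, giving 92%. The detectable HR is about 0.56.
- *Lenalidomide arm, 47 events, HR 0.15:* d₁ = 5.0, d₂ = 42.0, I = 4.44. Power = Φ(1.897 × 2.11 − 1.96) = Φ(2.04) = 98%.

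Schoenfeld would give 61% and 95% at HR 0.50, which leads to the same conclusion.

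**The case against.** **No inference about change is planned.** Section 9.8.2 says descriptive and hypothesis-generating, with no test and no interval. This stands. A reader might infer that the plan will attribute progression-related change to lenalidomide, or will do so at some calculable false-positive rate. The documents do not support that. Any such rate would need an assumed size of shift, which they do not give, and a test that the plan does not run. What remains is that a mixed quantity is a poor basis even for generating a hypothesis about the drug.

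**The samples cannot give a clean randomised comparison.** This stands too. A reader might infer that a valid randomised answer to 2.2.3.2 is available and simply not used. It is not: second samples are triggered by events whose timing and reason can differ by arm, and a death without prior progression gives no progression sample. Adding the observation arm removes one source of confusion, not all of them.

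**Observation patients are not excluded from SOX-2.** Only the power sentence names the lenalidomide arm; the statement that the association will be evaluated has no arm limit. Section 10.3 also expects a correlation with response to lenalidomide, which is a one-arm question. So the text does not support saying that observation-arm events are barred from the test. It supports saying that no such analysis is specified or powered.

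**Section 9.8.2 is not alone.** The GEP change analysis (9.8.1) and the MRI response analysis (9.8.3) are also restricted to lenalidomide patients. GEP is a fair contrast only for its prognostic analysis, which covers each arm and both combined.

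**One arm may be enough.** At the earlier study's HR of 0.15 it is. It is not enough if the true association is more moderate.

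**Conclusion.** The point holds as a gap in an exploratory correlative plan. The lenalidomide-only change cannot inform objective 2.2.3.2 because it combines drug effect, progression and elapsed time, while paired observation samples that would help are scheduled without a stated immune analysis. SOX-2 is sized on the arm expected to contribute about 39% of the PFS events. Using both arms raises power at HR 0.50 from about 52% to about 92% and moves the detectable HR from about 0.35 to about 0.56.

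These figures assume the plan's exponential medians, 33% prevalence, full sample yield, two-sided 5% (sidedness is not stated, but two-sided reproduces the plan) and one SOX-2 hazard ratio common to both arms. Lower yield would reduce both power figures; Section 9.8.4 assumes 55% for the cytogenetic samples. The progression argument extends a statement about MGUS-to-myeloma progression to this population. The primary and secondary clinical endpoints are not affected.

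**What to change.** Amend 9.8.2 in two places.

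1. **Immune change.** Replace the sentence on change with R therapy by text to this effect:

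> Change from baseline will be summarised by arm and by reason for the second sample (progression or other discontinuation), with time to sample shown. The R minus Obs difference, adjusted for the baseline value, will be reported with a 95% confidence interval, mainly for progression samples. Any contrast over all samples will be described as confounded by reason and timing. All of this is exploratory, and the R-only change will not be read as a drug effect.

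2. **SOX-2.** Specify an arm-stratified log-rank or Cox analysis of PFS in all randomised patients with a baseline sample. Give within-arm estimates and a SOX-2-by-arm interaction as secondary. Restate the power on about 123 events overall and about 47 in the lenalidomide arm, in place of half of 123 plus or minus 30%.

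The cost is a few sentences and a small amount of analysis. No patients, visits or samples are added, because the observation-arm specimens are already scheduled for the same laboratory. The downsides are a wider interval for a between-arm difference than for a one-arm change, and second samples from a non-random subset of each arm.
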